## **METHODS**

### **Risk recalculation**

Risk recalculation will be performed on all 954 consented FH-Risk women's data.

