### ***Estimation of Mammographic Density***

Mammograms will be assessed as near as possible to the time of first referral to the clinic and at the time of discharge (last clinic mammogram) or at the time of last visit if still under review. They will be assessed by the three methods used in the Tyrer-Cuzick model, (BIRADs, Volpara and an automated modification of the Visual Analogue Scale (Predictive VAS).

***BI-RADS*** (Breast Imaging-Reporting and Data System) will be reported according the system developed by American College of Radiology (5th Version 2013). Breast density is reported on a four point scale, a. breast is almost entirely fatty, b. scattered areas of fibroglandular density, c. heterogeneously dense breast, may obscure small masses and d. extremely dense breasts, lower the sensitivity of mammography. All mammograms will be double read by two experienced readers and if there is disagreement between readers a consensus is then reached. Training for consistency of reading will be by assessment of a series of 100 pairs of mammograms taken less than two weeks apart as previously described ([name] 2020). A third reader will assess the images if there is a discrepancy in BIRADs category. The final result will be incorporated in the Tyrer-Cuzick and the CanRisk models together with additional data required for risk estimation for each model.

***Volpara Volumetric Density*** (Volpara Health Technologies, Wellington, New Zealand) is a fully-automated method to estimate percentage volumetric density that requires commercial software and digital mammography DICOM files ("FOR PROCESSING" type). VolparaTM from Matakin is able to process images from a range of manufacturers (Hologic, GE, Siemens and Fuji). The method, in which knowledge of tissue attenuation coefficients, the physics of the imaging process and information in the DICOM header, are used to compute glandular thickness at each pixel position. VolparaTM uses a

relative physics model which reduces the need for accurate imaging physics data, but depends on locating a suitable fatty reference area within the image. VolparaTM outputs the fibroglandular tissue volume, total breast tissue volume, percentage of density by volume, and a Volpara Density Grade. We will be using the most recent software.

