The Volpara algorithm determines the X-ray attenuation between the image detector and the X-ray source, based on the pixel signals in the images. A pixel signal corresponding to purely adipose tissue is used as a reference to which all other pixels are compared, in order to calculate the thickness of adipose versus fibroglandular tissue that must have been present between the detector and the X-ray source. As the pixel dimensions are reported in the image, the volumes of adipose and fibroglandular tissue are then summed across the entire breast. VBD is calculated as the ratio of fibroglandular tissue volume to total breast volume, expressed as a percentage. This quantitative VBD value is then mapped to a FDA cleared VDG (i.e. an automated equivalent of the BI-RADS 5th edition density categories) using pre-set thresholds.

**Predictive VAS** – Members of the research team ([name]) have built convolutional neural networks (CNN) to predict density VAS scores from full-field digital mammograms. The CNNs are trained using whole-image mammograms, each labelled with the average VAS score of two independent readers. Each CNN learns a mapping between mammographic appearance and VAS score so that at test time, they can predict VAS score for an unseen image. Networks were trained using 67,520 mammographic images from 16,968 women and for model selection we used a dataset of 73,128 images. There was no significant difference between reader VAS and predicted VAS for the prior test set (likelihood ratio chi square,  $p=0.134$ ). The fully automated method shows promising results for cancer risk prediction and is comparable with human performance (Ionesco 2018).

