#### Secondary

- i) To compare the risk profiles for TCv8 for different measures of mammographic density (BIRADS, Volpara and predicted VAS) (BOADICEA V5 – CanRisk uses only the BIRADS to assess MD).
- ii) To determine the reproducibility and validity of two readers of BIRADS

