- iv) **Comparison of mammographic density methods and the relationship with TCv8 risk scores** – scatterplots, intraclass correlation coefficients and Bland-Altman plots will be used to look at the relationship between different mammographic density methods. Risk scores will also be compared for TCv8 using different methods for measuring mammographic density to determine the impact this has on overall risk score. Changes in NICE risk categories will be compared using the different methods using the McNemar-Bowker test and differences in the continuous risk measures will be compared using repeated measures analysis of variance (ANOVA).

- v) **Reader reproducibility for BIRADS** - reproducibility for readers assessing BIRADS score will be determined using inter-reader and intra-reader statistics, using the McNemar-Bowker test to assess agreement within and between readers.

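### BI-RADS reader agreement is to be judged with the McNemar-Bowker test, which does not measure agreement; the data for the intra-reader part and the analysis for validity are not identified

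*Combined protocol and SAP*

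**What the plan says.** The secondary objective in the Statistical Analysis Plan (section 3.1, Objectives, Secondary, ii) is "To determine the reproducibility and validity of two readers of BIRADS". Section 2.2, objective iv, says the same.

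The matching analysis is item v under 3. Analysis: "reproducibility for readers assessing BIRADS score will be determined using inter-reader and intra-reader statistics". It names the McNemar-Bowker test as the tool for agreement both within and between readers. It gives no kappa or other agreement coefficient, no confidence interval, and no statement of which reads are used.

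The reading procedure is under Estimation of Mammographic Density: "All mammograms will be double read by two experienced readers and if there is disagreement between readers a consensus is then reached". A further sentence adds: "A third reader will assess the images if there is a discrepancy in BIRADs category". Paired images are mentioned only once: "Training for consistency of reading will be by assessment of a series of 100 pairs of mammograms taken less than two weeks apart".

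The secondary endpoint and item iv compare visual BI-RADS, Volpara and predicted VAS as methods. Volpara produces a density grade that the protocol describes as "an automated equivalent of the BI-RADS 5th edition density categories".

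**The concern.** Item v raises three separate problems.

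1. **The test does not answer the question.** McNemar-Bowker asks whether reader A grades above reader B as often as below, for each pair of grades. It ignores the diagonal of the table, where agreement lies. Readers who disagree often but evenly would give a non-significant result that could be reported as good reproducibility. Conversely, with many pairs, a small one-sided shift can be significant although exact agreement is high.
2. **The intra-reader data are not identified.** A within-reader statistic needs the same reader to grade the same breasts twice over a short interval. The scheme for the study mammograms does not describe that.
3. **Validity has no analysis.** Item v deals only with reproducibility, and no reference for the readers is named.

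BI-RADS is the only density measure that BOADICEA V takes, and it is the density measure named in the primary endpoints for both models. A reader-agreement result that cannot detect poor agreement would give false reassurance about that input.

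**Working it through.** The documents give no sample size, precision or expected agreement for item v, so there is no planned figure to reproduce. The check counts the reads and then looks at what the named test measures.

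**Step 1: reads available.** Inputs:
- Women: "Risk recalculation will be performed on all 954 consented FH-Risk" participants.
- Time points per woman: two. "Mammograms will be assessed as near as possible to the time of first referral to the clinic and at the time of discharge", or at the last visit if the woman is still under review.
- Readers per mammogram: two.

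The upper bound, if both mammograms exist for every woman:
- Mammograms: 954 × 2 = 1,908
- Reads: 1,908 × 2 = 3,816
- Inter-reader pairs: 1,908
- Same-reader repeat pairs: 0

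The consensus or third-reader step does not add an independent second read by the same reader. A woman's two mammograms cannot serve as repeats either, because her density can change between first referral and discharge or last visit.

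**Step 2: what McNemar-Bowker measures.** The statistic is the sum, over pairs of grades i < j, of (n_ij − n_ji)² / (n_ij + n_ji). It is 0 for any symmetric table. Take an illustrative table for four grades, with 10 in each diagonal cell, 15 in each cell one grade off, and 0 elsewhere:
- Total: 4 × 10 + 6 × 15 = 130
- Exact agreement: 40/130 = 30.8%
- Margins: 25, 40, 40, 25 for each reader
- Chance agreement: (25² + 40² + 40² + 25²)/130² = 4,450/16,900 = 26.3%
- Unweighted kappa: (0.3077 − 0.2633)/(1 − 0.2633) = 0.06
- Bowker statistic: 0, p = 1

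In a more extreme case, all 16 cells are equal. Exact agreement is then 4/16 = 25%, which is the chance level. Kappa is 0 under any weighting, and Bowker is again 0.

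**Step 3: why the weights must be fixed in advance.** In the 130-read table every disagreement is by one grade, so the mean observed disagreement is 90/130 = 0.692 under linear or quadratic weights.
- Linear weights: expected disagreement from the margins 18,950/16,900 = 1.121; kappa = 1 − 0.692/1.121 = 0.38
- Quadratic weights: expected disagreement 2 × (132.5/130) = 2.038; kappa = 1 − 0.692/2.038 = 0.66

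The same table therefore gives 0.06, 0.38 or 0.66.

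**Step 4: whether the consensus grade could be the validity reference.** Where the readers agree, the consensus equals both reads. If adjudication picks one of the two reads (an assumption) and inter-reader agreement is p, mean reader agreement with the final grade is p + (1 − p)/2. For assumed p of 60%, 70%, 80% and 90% this is 80%, 85%, 90% and 95%. The figure follows from p alone and says nothing about validity.

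**Step 5: precision from the 100 pairs.** The 95% half-width for percent agreement is 1.96 × √(p(1 − p)/100). At assumed within-reader agreement of 70%, 80% and 90% it is ±9.0, ±7.8 and ±5.9 percentage points per reader.

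**The case against.** The strongest reply is that the gap is one of wording. Inter-reader agreement is fully available from the double reads. The 100 training pairs are near-repeats that could supply the within-reader data, and item v does not exclude them. One read per reader is the natural meaning of the reading procedure, but the text does not rule out a re-read. Item iv already sets BI-RADS against Volpara and predicted VAS, which bears on validity at method level. The risk models use the final grade after consensus or third read, so single-reader error does not translate directly into noise in the risk categories.

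All of this stands, and it limits the point. A reader might infer that the reproducibility and validity objective cannot be delivered by this design. The documents do not support that, because existing material could deliver the reproducibility part once it is named, and a comparator grade for validity exists at least for some images. A reader might also infer that reading error distorts the primary category changes. No such effect can be shown from the documents.

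The reply leaves the choice of test unanswered. Whichever reads are used, McNemar-Bowker does not measure agreement. Item iv does not evaluate either reader and is not tied to the reader objective.

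**Conclusion.** The point holds in a limited form. McNemar-Bowker is the wrong measure for agreement within or between readers: it returns 0 for every symmetric table, including one with chance-level agreement. That conclusion is algebraic and needs no assumption about this study.

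The study reads as described supply up to 1,908 inter-reader pairs and no intra-reader pairs. This rests on reading the double-read procedure as one read per reader, and on both mammograms being available for all 954 women for the upper bound. The 100 training pairs are the only near-repeat material described, and no analysis names them. Validity is promised twice without an analysis under that name.

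The consequence is confined to a secondary objective, and the remedy is inexpensive. The documents give no basis for predicting the kappa that will be observed, and they do not say whether the training images come from the study set.

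**What to change.** Rewrite item v as follows.

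- **Agreement measure:** weighted kappa with a 95% confidence interval, the weights (linear or quadratic) stated in advance. Keep McNemar-Bowker only as a check for systematic shift between readers.
- **Inter-reader:** computed on the two reads made before consensus or third read.
- **Intra-reader:** computed for each reader on the 100 pairs, read blind to pairing, with the grades retained. State two limits: the pairs are different images, so repositioning is mixed with reader error, and reads made in training may differ from later study reads.
- **Validity:** either report each reader's weighted kappa against the Volpara density grade, labelled as agreement with an automated measure, or delete the word from section 2.2, objective iv, and from the SAP secondary objective. If the Volpara route is taken, restrict it to mammograms with the raw (for-processing) files that Volpara needs and report how many there are. Section 3.1 says raw images had not been kept at an earlier stage, and the documents do not say how many are affected.

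The cost is SAP wording, plus keeping the pre-consensus reads and the training grades. No further reads are needed if the 100 pairs are graded blind to pairing during training.

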## 3. Analysis

The primary analysis will compare the risk categories and risk scores for the risk prediction models for women at entry to the clinic (or age 40) and at last follow-up in the clinic, and will compare the risk scores given by TCv8 and BOADICEA using different model inputs.

- i) **Change in risk categories** – NICE risk categories (average, moderate and high) will be compared by creating cross tabulations of risk categories at entry and at last follow-up – the number (and percentage) of women moving up and down risk categories will be

reported and the McNemar-Bowker test will be used to determine whether the change in risk categories is statistically significant between the two time points.

- ii) **Change in 10-year and lifetime risk scores** - change in continuous risk measures (10-year and lifetime risk estimates) will be estimated from TCv8 and BOADICEA risk prediction models. Normality and skewness of 10-year and lifetime breast cancer risk scores will be assessed. Where there is evidence of non-normality scores will be transformed. Scatterplots and correlation coefficients will be used to examine the relationship between 10-year and lifetime risk estimates at baseline and at latest follow-up.

Descriptive statistics will be used to report change in risk scores from time at entry to latest follow-up and will be compared using a paired t-test. Linear regression will be used to determine which risk factors (e.g. SNP313, MD) are associated with change in risk score.

- iii) **Comparison between risk models** - descriptive statistics will be used to report risk scores from TCv8 and the BOADICEA models and differences in risk scores compared. Models will be compared using a) classical risk factors alone, b) classical risk factors plus mammographic density, as measured by BIRADS, which can be included in both models and c) classical risk factors plus mammographic density and SNPs. Scatterplots and correlation coefficients will be used to examine the relationships between models and Bland-Altman plots used to show the agreement between the models.

Secondary analysis will focus on the comparison between differences in mammographic density measures and the relationship with risk scores using TCv8.

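### The only method named for BI-RADS reader agreement, the McNemar-Bowker test, tests whether disagreements are symmetric and cannot show how well the readers agree

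*Combined protocol and SAP*

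**What the plan says.** Secondary objective ii of the SAP is "To determine the reproducibility and validity of two readers of BIRADS". The analysis that serves it is item v of section 3 (Analysis), where reproducibility "will be determined using inter-reader and intra-reader statistics, using the McNemar-Bowker test to assess agreement within and between readers". The inter-reader and intra-reader statistics are not identified. McNemar-Bowker is the only procedure named, and the sentence gives it the task of assessing agreement.

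The reading design is under Estimation of Mammographic Density in section 3.1. "Breast density is reported on a four point scale". "All mammograms will be double read by two experienced readers and if there is disagreement between readers a consensus is then reached". "A third reader will assess the images if there is a discrepancy in BIRADs category". The final value then enters both Tyrer-Cuzick and CanRisk. For training, "Training for consistency of reading will be by assessment of a series of 100 pairs of mammograms taken less than two weeks apart"; no agreement statistic is attached to that exercise.

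Elsewhere the SAP does name agreement measures. For the risk models (item iii) it has "Bland-Altman plots used to show the agreement between the models". For the density methods (item iv), "intraclass correlation coefficients and Bland-Altman plots will be used to look at the relationship between different mammographic density methods". Neither covers the BI-RADS readers.

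**The concern.** McNemar-Bowker is a test of symmetry. It suits a question about shift, and item i uses it that way for movement between NICE categories over time. Reader agreement is a different question: how often, and how closely, two readings of the same image coincide. A non-significant result does not show that readers agree, because readers who agree only by chance produce one whenever they use the categories in similar proportions. A significant result shows a systematic difference, but neither its size nor the overall agreement, and in a large sample it can come from readers who agree on well over 90% of images.

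At stake is the reproducibility half of secondary objective ii. BI-RADS is also the density input common to both models in the primary comparison, so anyone using the results will want to know how reproducible it is.

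**Working it through.** The plan gives no sample size, significance level, target agreement or expected category shares for this analysis, so there is no figure of its own to reproduce. The check is of what the named test can measure.

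**Inputs.** From the documents: four ordered categories; two readers per mammogram; 100 training pairs; 271 women still in follow-up; 954 women in the cohort. Assumed: all cell counts and category shares below, and alpha 0.05 in the simulations.

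**Formula.** For a 4x4 table with counts n_ij (first reading i, second reading j),

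chi-square = sum over i<j of (n_ij − n_ji)² / (n_ij + n_ji),

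with 4×3/2 = 6 degrees of freedom (df), or fewer if empty cell pairs are dropped. The agreeing cells n_ii do not appear. This is algebra and holds for any table.

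**Same p-value, opposite agreement (n = 960).**
- All 16 cells equal to 60: agreement 4×60/960 = 25%, kappa 0. Every n_ij = n_ji, so chi-square = 0 and p = 1.0.
- Diagonal cells 225, the other twelve cells 5: agreement 900/960 = 93.75%. The category distances of the twelve off-diagonal cells sum to 6×1 + 4×2 + 2×3 = 20. Observed mean distance is 20×5/960 = 0.104; expected by chance with equal margins it is 20/16 = 1.25. Linear kappa = 1 − 0.104/1.25 = 0.92. Chi-square is again 0 and p = 1.0.

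**Same significant result, different agreement.** Take neighbouring-category disagreements of 12/6, 24/8 and 22/8. Chi-square = 6²/18 + 16²/32 + 14²/30 = 2.00 + 8.00 + 6.53 = 16.53; p = 0.0009 on 3 df, 0.011 on 6 df.
- With diagonal 90/370/360/54 (n = 954): agreement 874/954 = 92%, linear kappa 0.90.
- With diagonal 10/20/20/5 (n = 135): agreement 55/135 = 41%, linear kappa 0.41.

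**Two extremes at n = 954.**
- Diagonal 92/366/366/94 with 36 disagreements all in one direction (8, 20, 8): agreement 918/954 = 96.2%, unweighted kappa 0.94, chi-square = 8 + 20 + 8 = 36, p = 2.8×10⁻⁶ on 6 df.
- Readers who never agree but disagree symmetrically (100/100, 277/277, 100/100): agreement 0%, unweighted kappa −0.50, p = 1.0.

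**Behaviour by sample size (20,000 simulated tables per scenario).** Assumed category shares were 10/40/40/10, 5/30/45/20, 25/25/25/25 and 15/45/30/10.

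Chance-only readers with the same shares have 25–34% agreement and kappa 0. They are non-significant in about 95–97% of tables at n = 100, 271 and 954. This depends on matching shares: with 10/40/40/10 against 5/30/45/20, the test rejects in 38%, 91% and 100%.

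Readers with 93–94% exact agreement (linear kappa 0.92–0.95) and a small shift (6% one category up, 2% down) are significant as follows:

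| n | Empty pairs dropped | 6 df |
|---|---|---|
| 100 | 5–13% | about 0% |
| 271 | 30–62% | 5–20% |
| 954 | 91–100% | 70–98% |

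The test is right to detect that shift. But the p-value moves with n while agreement stays the same. In this scenario 95% of sampled linear kappas lie within about 0.85–0.98 at n = 100 and 0.90–0.96 at n = 954, so kappa is informative at these sizes.

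**The case against.** The strongest reply is that the opening reference to inter-reader and intra-reader statistics is broad enough to include kappa and percent agreement, so the fault is a loose sentence and not an unanswerable objective. An analyst could well add kappa, and any 4x4 reader table would yield it later without new data. But none is named, and the sentence goes on to give the assessment of agreement to McNemar-Bowker. Followed literally, a symmetry p-value would be reported as agreement.

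Second, the consequence is small. Adjudicated values enter the models regardless, reader reproducibility is not listed among the secondary endpoints, and no pass rule depends on it. That stands and limits the point to this objective.

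Third, the illustrations are not this study's data. Chance-level reading is implausible for trained, experienced readers. With two examinations per woman, there could be up to 2×954 = 1,908 double-read examinations. This is fair: the simulated percentages describe the test, not an expected result here. The algebra needs none of them.

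Two limits also stand. Objective ii includes validity, which between-reader kappa does not address. And the double read supplies inter-reader data only; the documents do not say which readings will serve the intra-reader comparison that item v promises.

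**Conclusion.** The concern holds. Item v names a method that is wrong for its stated purpose: the McNemar-Bowker statistic omits the agreeing cells, so it cannot measure agreement, and the plan names no other reader measure. In exact tables p = 1.0 accompanies both 25% and 93.75% agreement, and chi-square 16.53 accompanies both 92% and 41%. The conclusion rests on the formula alone; the tables and simulations use assumed counts and shares.

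This should be fixed, but its reach is limited to the reproducibility part of secondary objective ii. The primary comparisons of categories and risk scores do not depend on it. The risk is misinterpretation of the reader result.

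**What to change.** In item v, name weighted kappa (stating linear or quadratic weights) with a 95% confidence interval, and percent exact agreement, as the agreement measures for both the inter-reader and the intra-reader comparison. Present the 4x4 reader table with them. Specify that the reads are those made before consensus or third-reader adjudication, since afterwards disagreements have been resolved to one value. State the n and the source of the readings for each comparison. Keep McNemar-Bowker only as a labelled check for systematic difference between readings.

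The cost is one or two sentences. The inter-reader measures use the double reads already planned, and the intra-reader measures need no readings beyond those item v already implies.
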